## 5.2. Exclusion Criteria

Participants are excluded from the study if they meet ANY of the following criteria:

12. Prior treatment with abemaciclib or any CDK4 and/or CDK6 inhibitors.

13. Currently enrolled in a clinical study involving an investigational product or any other type of medical research judged not to be scientifically or medically compatible with this study. Have participated in any clinical trial for which treatment assignment is still blinded unless agreed by the Lilly CRP/CRS. If a participant is currently enrolled in a clinical trial involving non-approved use of a device, then agreement with the investigator and the Lilly CRP/CRS is required to establish eligibility.
14. Have a history of any other cancer (except nonmelanoma skin cancer or carcinoma in-situ of any origin), unless in complete remission with no therapy for a minimum of 2 years.
15. Serious and/or uncontrolled preexisting medical condition(s) including but not limited to severe renal impairment (for example, estimated creatinine clearance <30 mL/min), severe hepatic impairment (Child-Pugh C), interstitial lung disease (ILD)/pneumonitis, severe dyspnea at rest or requiring oxygen therapy. Other serious preexisting medical condition(s) that, in the judgment of the investigator, would preclude participation in this study (such as history of major surgical resection involving the stomach or small bowel, or preexisting Crohn's disease or ulcerative colitis, preexisting chronic condition resulting in Grade  $\geq 2$  diarrhea, gastrointestinal disorder affecting absorption or inability to swallow medication).
16. History of any of the following conditions within the last 12 months: syncope of cardiovascular etiology, ventricular arrhythmia of pathological origin (including, but not limited to, ventricular tachycardia and ventricular fibrillation), or sudden cardiac arrest.
17. The participant has active systemic infections (for example, bacterial infection requiring intravenous [IV] antibiotics at time of initiating study treatment, fungal infection, or detectable viral infection requiring systemic therapy) or viral load (such as known human immunodeficiency virus positivity or with known active hepatitis B or C [for example, hepatitis B surface antigen positive]). Screening is not required for enrollment.
18. Known or suspected central nervous system (CNS) metastatic disease (baseline screening for CNS metastases is not required unless there is presence of signs and/or symptoms of CNS involvement).
19. Untreated spinal cord compression or evidence of spinal metastases with risk of spinal compression. Structurally unstable bone lesions suggesting impending fracture.
20. Estimated life expectancy < 4 months as assessed by the investigator.

### 5.3. Lifestyle Considerations

- Participants should refrain from consuming grapefruits or grapefruit juice while on study intervention.
- Participants must not take preparations or herbal products thought to affect PSA levels (such as, saw palmetto or pomegranate).
- Participants must not donate blood or sperm during the study and for 3 months after the last study intervention dose.
- Participants with known hypersensitivity or suspected intolerance to abemaciclib or any of its excipients (e.g., lactose) should not take abemaciclib unless deemed appropriate by the investigator.

See Section [6.5](#) for additional guidance on concomitant therapy.

### 5.4. Screen Failures

Screen failures are defined as participants who consent to participate in the clinical study but are not subsequently enrolled in the study. A minimal set of screen failure information is required to ensure transparent reporting of screen failure participants to meet the Consolidated Standards of Reporting Trials publishing requirements and to respond to queries from regulatory authorities. Minimal information includes demography, screen failure details, eligibility criteria, and any SAEs.

The following participants may be eligible for re-screening:

- Participants who become eligible to enroll in the study as a result of a protocol amendment.
- Participants whose status has changed such that the eligibility criterion that caused the participant to screen fail would no longer cause the participant to fail screening again (e.g., unexpected surgery during the screening period that is no longer relevant following recovery from surgery).
- A patient who completes screening and meets all inclusion and exclusion requirements but is unable to be enrolled due to extenuating circumstances (such as severe weather, death in family, child illness).

The interval between rescreening should be  $\geq 2$  weeks. Individuals may be rescreened a maximum of 2 times. The individual must sign a new ICF and will be assigned a new identification number.

Repeating laboratory testing during the screening period or repeating screening tests to comply with the protocol designated screening period does not constitute rescreening.

## 6. Study Intervention

Study intervention is defined as any investigational intervention(s), marketed product(s), placebo, or medical device(s) intended to be administered to a study participant according to the study protocol. In CYCLONE 1, study intervention is defined as the administration of abemaciclib.

### 6.1. Study Intervention(s) Administered

Abemaciclib will be administered at a starting dose of 200 mg orally twice daily with a minimum of 6 hours between doses, at approximately the same time every day. Abemaciclib should be swallowed whole with a glass of water (do not chew, crush, split, dissolve in water, or alter in any way prior to swallowing). Abemaciclib may be taken with or without food.

If a participant misses a dose at the scheduled time for nonmedical reasons, the dose should be taken as soon as possible on the same day and then twice-daily administration should be resumed (with at least 6 hours separating doses). If a participant vomits after taking a dose, then the dose should not be retaken and the next dose should be taken at the usual scheduled time.

The investigator or his/her designee is responsible for the following:

- Explaining the correct use of the drug and planned duration of each individual's treatment to the participant/study-site personnel/legal representative.
- Verifying the instructions are followed properly.
- Maintaining accurate records of abemaciclib dispensing and collection.
- Returning all unused medication to Lilly, or its designee at the end of the study, unless the site is authorized by Lilly or its designee to destroy unused medication, as allowed by local law.

Study Intervention	Dose	Treatment Schedule	Route of Administration
Abemaciclib	200 mg	Twice daily	Oral

### 6.2. Preparation/Handling/Storage/Accountability

The investigator or designee must confirm appropriate temperature/storage conditions have been maintained during transit for all study intervention received and any discrepancies are reported and resolved before use of the study intervention.

Only participants enrolled in the study may receive study intervention and only authorized study personnel may supply study intervention. All study intervention must be stored in a secure, environmentally controlled, and monitored (manual or automated) area in accordance with the labeled storage conditions with access limited to the investigator and authorized study personnel.

The investigator, or authorized study personnel, is responsible for study intervention accountability, reconciliation, and record maintenance (that is, receipt, reconciliation, and final disposition records).

Further guidance and information for the final disposition of unused study interventions are provided in the Pharmacy Manual.

#### **6.2.1. Selection and Timing of Doses**

A treatment cycle is defined as an interval of 28 days. Abemaciclib will be administered orally twice daily at approximately the same times each day on Days 1 through 28 of a 28-day cycle ( $\pm 3$  days). Details on treatment administration are described in Section 6.1. In the event of a dose suspension due to toxicity immediately prior to the beginning of a cycle, the PK sampling schedule outlined in Section 1.3.1 may require adjustment and the sponsor should be notified.

A cycle delay or earlier start due to logistical reasons (for example, due to holiday, weekend, inclement weather, or other unforeseen circumstances), will be permitted for up to a maximum of 7 days (and not be considered a protocol violation). In exceptional cases, such as planned delays (including but not limited to vacation or holidays), additional study treatment may be dispensed after discussion with Lilly CRP/CRS.

Participants may continue to receive study intervention until evidence of disease progression, or any discontinuation criteria are met (See Section 7).

#### **6.3. Measures to Minimize Bias: Randomization and Blinding**

This is a non-randomized, open-label study.

#### **6.4. Study Intervention Compliance**

Participant compliance with study intervention will be assessed at each cycle. Compliance will be assessed by counting returned tablets. Study medication administration data will be recorded in the participant's medical record and eCRF. Deviation(s) from the prescribed dosage regimen should be recorded in the eCRF.

Participants who are significantly noncompliant will be discontinued from the study after discussion with Lilly CRP/CRS. A participant will be considered significantly noncompliant if he missed more than 7 consecutive days of study medication (full dose) or more than 25% cumulative days of study medication (full dose). Similarly, a participant may be considered significantly noncompliant if he is judged by the investigator to have intentionally or repeatedly taken more than the prescribed amount of medication. Abemaciclib dose suspensions or delays related to toxicity may occur and will not result in a participant being considered noncompliant.

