Symptomatic Progression			X		X		X	X	X	
Assess:
 
 
• Symptomatic skeletal event defined as symptomatic fracture, surgery, or radiation to bone or spinal cord compression
 
• Pain progression or worsening of disease-related symptoms requiring initiation of a new systemic anti-cancer therapy
 
• Development of clinically significant symptoms due to loco-regional tumor progression requiring surgical intervention or radiation therapy
 
 
Perform until evidence of symptomatic disease progression, start of new anticancer therapy, withdrawal of consent, death, or study completion, whichever occurs first.

Study Treatment										

Screening, On-Treatment and Post-Treatment Schedule of Activities										
Study phases	Screening		On Treatment Cycle duration = 28 days				Post-Treatment Follow-up		Instructions	
	Baseline		Cycle 1		Cycle 2		Cycle 3 and subsequent	Short-Term Follow-Up a	Long-Term Follow-Up b	Instructions
Relative Day within Dosing Cycle & Visit Window ( $\pm n$ days)	$\le 28$	$\le 14$	D1 ( $\pm 3$ )	D15 ( $\pm 3$ )	D1 ( $\pm 3$ )	D15 ( $\pm 3$ )	D1 ( $\pm 3$ )	V801 (30 days $\pm 7$ )	V802-8XX (90 days $\pm 14$ )	Procedures and disease assessments (tumor imaging) should be performed as per the schedule of activities, according to the calendar days, regardless of treatment delays.
Abemaciclib			Orally twice daily, on Days 1 through 28 of a 28-day cycle.						See Section 6.1	
Study Drug Compliance Assessment				X			X			
Review Patient Diary			X	X	X	X				Review patient diary at each study visit for completion of date and time for each dose taken on the day before PK sampling. After Cycle 3 Day 1, the diary is no longer required.
Post-study Treatment Collections										
Post-Discontinuation Anti-Cancer Therapies							X	X	Collect until death, withdrawal of consent, or study completion.	
Survival Status							X	X	Although preferable to collect during a clinic visit, if no procedures are required, survival information may be collected by contacting the patient or family directly (e.g., via telephone. This should be collected at minimum every 90 ( $\pm 14$ ) days if no other procedures are performed.	

Screening, On-Treatment and Post-Treatment Schedule of Activities									
Study phases	Screening		On Treatment Cycle duration = 28 days			Post-Treatment Follow-up		Instructions	

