Abbreviations: AE = adverse event; CNS = central nervous system; CT = computed tomography; CTC = circulating tumor cells; CTCAE = Common Terminology Criteria for Adverse Events (NCI 2017); D = day; ECG = electrocardiogram; ECOG = Eastern Cooperative Oncology Group (Oken et al. 1982); EORTC-QLQ-C30 = European Organization for the Research and Treatment of Cancer Quality of Life Questionnaire; FACT-GP5 = Functional Assessment of Cancer Therapy- General; MRI = magnetic resonance imaging; n = number; NRS = numeric rating scale; PD = pharmacodynamics; PGx = pharmacogenomics; PK = pharmacokinetics; PRO = patient-reported outcome; PRO-CTCAE = Patient-reported outcome Common Terminology Criteria for Adverse Events; PSA = prostate specific antigen; QoL = quality of life; SAE = serious adverse event; V = visit.

a Short-term follow-up begins when the participant and investigator agree that the participant will no longer continue study treatment and lasts approximately 30 days ( $\pm 7$  days).

b Long-term follow-up begins when the short-term follow-up period is completed and continues until the participant's death, loss to follow-up, or study withdrawal.

In all cases, no follow-up procedures will be performed for a participant who withdraws informed consent unless he has explicitly provided permission and consent.

Mobile healthcare service may be leveraged to collect and process lab samples in conjunction with a patient's visit, when deemed appropriate by the investigator and allowed by local laws and regulations.

Continued Access Schedule of Activities			
Study phase	Continued Access Treatment	Follow-up a	Instructions
	V501-V5XX	V901	
Procedure			
Abemaciclib	X		Orally twice daily on Days 1 through 28 of a 28-day cycle.
AE collection	X	X	
Assessments to be conducted at a minimum with each collection and dispensing study drug (every 28 days) from Visits 501-5XX. After V801, only SAEs that are related to study intervention or protocol procedure will be collected.
 
Frequency of evaluation, including efficacy assessments, is left to the judgement of the investigator based on standard of care.

Abbreviation: AE = adverse event; SAE = serious adverse event; V = visit.

a Continued access follow-up begins when the patient and the investigator agree that the patient will no longer continue abemaciclib in the continued access period and lasts approximately 30 days.

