## 7. Discontinuation of Study Intervention and Participant Discontinuation/Withdrawal

### 7.1. Discontinuation of Study Intervention

Participants may discontinue the study intervention at any time for any reason. Investigators should try to find out the reason and document it on the corresponding CRF.

The reason and date of discontinuation will be collected for all participants.

Participants with PSA-only progression should continue study intervention until disease progression (radiographic and/or symptomatic progression), when participant safety is not compromised.

Study intervention should be continued for as long as the participant consents and complies with study procedures and requirements, is tolerating the study intervention, until radiographic progression according to RECIST 1.1 for soft tissue and/or PCWG3 for bone; and/or until symptomatic progression.

Symptomatic progression is defined as:

- Symptomatic Skeletal Event (SSE), defined as symptomatic fracture, surgery or radiation to bone, or spinal cord compression
- Pain progression or worsening of disease-related symptoms requiring initiation of a new systemic anti-cancer therapy.
- Development of clinically significant symptoms due to loco-regional tumor progression requiring surgical intervention or radiation therapy.

When study intervention is discontinued due to symptomatic progression, the investigator should obtain CT/MRI and bone scan imaging within 14 days to assess for radiographic progression, prior to the participant initiating radiotherapy, surgery or subsequent anti-cancer therapy (whichever comes first).

Patients discontinuing study intervention due to documented radiographic progression will be followed for the development of symptomatic progression until start of new anticancer therapy, withdrawal of consent, death, or study completion, whichever occurs first.

Participants discontinuing study intervention prior to documented radiographic progression will continue to have scheduled disease assessments until documented radiographic progression, start of new anticancer therapy, withdrawal of consent, death, or study completion, whichever occurs first.

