All participants discontinuing study intervention will have procedures performed as shown in Section 1.3 and enter the short-and-long-term follow-up periods and will be followed for the initiation of subsequent anti-cancer therapies and survival status every 3 months until death, loss of follow-up, or withdrawal of consent, whichever comes first.

Participants will be discontinued from study intervention in the following circumstances:

- the participant or the participant's designee (for example, parents or legal guardian) requests to be discontinued from study intervention
- sponsor decision
- investigator decision
- the participant is enrolled in any other clinical trial involving an investigational product or other type of medical research judged not to be scientifically or medically compatible with this study
- radiographic or symptomatic disease progression as discussed above
- the participant, for any reason, requires treatment from another therapeutic agent that has been demonstrated to be effective for treatment of the study indication. Discontinuation from study intervention will occur prior to introduction of the new agent.
- the participant experiences unacceptable toxicity
- the participant is significantly noncompliant with study procedures and/or intervention.

In exceptional circumstances, a participant may continue study intervention beyond disease progression if there is no effective alternative therapy and the participant, in the opinion of the investigator, is receiving clinical benefit from the study drug. In these rare cases, the investigator must obtain documented approval from the Lilly CRP/CRS to allow the patient to continue study intervention. Additionally, the patient must reconsent prior to continuing to receive study intervention.

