## **7.2. Participant Discontinuation/Withdrawal from the Study**

A participant will be discontinued from the study in the following circumstances:

- participation in the study needs to be stopped for medical, safety, regulatory, or other reasons consistent with applicable laws, regulations, and good clinical practice (GCP)
- at any time at the participant's own request
- at the request of the participant's designee (for example, parents or legal guardian)
- at the discretion of the investigator

At the time of discontinuing from the study, if possible, an early discontinuation visit should be conducted, as shown in the SoA (Section 1.3). The participant will be permanently discontinued both from the study intervention and from the study at that time.

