### **7.3. Lost to Follow up**

A participant will be considered lost to follow-up if he repeatedly fails to return for scheduled visits and is unable to be contacted by the study site. Site personnel or designee are expected to make diligent attempts to contact participants who fail to return for a scheduled visit or were otherwise unable to be followed up by the site.

Site personnel, or an independent third party, will attempt to collect the vital status of the participant within legal and ethical boundaries for all participants who initiate treatment. Public sources may be searched for vital status information. If vital status is determined to be deceased, this will be documented, and the participant will not be considered lost to follow-up. Lilly personnel will not be involved in any attempts to collect vital status information.

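### Protocol 6.4 takes significantly noncompliant participants off the study, 7.1 only off study drug; read literally, 6.4 can cut short follow-up for secondary endpoints (minor)

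*Protocol*

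**What the plan says.** **Section 6.4 of the protocol** sets the consequence of poor drug compliance: "Participants who are significantly noncompliant will be discontinued from the study after discussion with Lilly CRP/CRS". The trigger is more than 7 consecutive days, or more than 25% of cumulative days, of missed study medication. Repeated or intentional over-dosing may also count. Suspensions for toxicity are exempt.

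**Section 7.1** has a list of reasons for stopping study intervention, which includes "the participant is significantly noncompliant with study procedures and/or intervention". Stopping drug does not end follow-up there: "Participants discontinuing study intervention prior to documented radiographic progression will continue to have scheduled disease assessments until documented radiographic progression", unless new anticancer therapy, withdrawal of consent, death or study completion comes first. Everyone who stops drug is also followed for later therapies and for "survival status every 3 months until death, loss of follow-up, or withdrawal of consent". The Schedule of Activities (Section 1.3) has its own stopping rule for symptomatic-progression checks: "Perform until evidence of symptomatic disease progression, start of new anticancer therapy, withdrawal of consent, death, or study completion". Noncompliance is not in that rule.

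**Section 7.2** treats leaving the study as a separate status, with one early discontinuation visit if possible: "The participant will be permanently discontinued both from the study intervention and from the study at that time". Its list of reasons does not name noncompliance, but it includes other reasons consistent with law and good clinical practice, and investigator discretion. Footnote b of the Schedule of Activities reads: "Long-term follow-up begins when the short-term follow-up period is completed and continues until the participant's death, loss to follow-up, or study withdrawal".

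**The concern.** Two operative rules attach different consequences to overlapping conduct. One site could follow 6.4 and close out a participant; another could follow 7.1 and keep scanning a similar one.

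At stake is the follow-up behind several secondary endpoints. If scans stop, rPFS is censored at the last adequate assessment (SAP Table JPCY.6.1), and duration of response follows the same rules (SAP 6.7.2.3). Time to symptomatic progression is censored at the last date without progression (SAP 6.7.2.7). A man who misses more than a week of tablets may be deteriorating, or he may be well and careless. If the reason is related to prognosis, the censoring is informative.

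**Working it through.** **The two readings side by side**

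| Item | 7.1: off drug | 6.4 read with 7.2 and footnote b: off study |
|---|---|---|
| Study drug | stops | stops |
| Scans | continue to progression, new therapy, consent withdrawal, death or study completion | can end at removal |
| Symptomatic-progression checks | continue under the Schedule of Activities rule | can end at removal |
| Survival contacts | every 3 months | can end; vital-status search under 7.3 remains |
| Best overall response | through short-term follow-up visit | same window |

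**Plan's own figures.** The rule of 5 or more responders in 40 gives P(X ≥ 5 | 40, 0.05) = 0.048 and P(X ≥ 5 | 40, 0.15) = 0.737. Both match the stated 4.8% and 73.7%. The compliance wording does not enter either figure.

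**Size of the rPFS shift: inputs**
- n = 40 (Protocol 9.2).
- Number removed, k = 0 to 3: assumed, since the documents give no noncompliance rate. f = k/40, at most 0.075.
- Hazard of removed participants relative to the rest, h = 0.5 to 2: assumed.
- Median rPFS 3.7 months under complete follow-up: the CARD anti-androgen arm (Protocol 4.2), a less pretreated population.
- Removal time: just after the Week 9 scan, day 56, so tr = 56/(365/12) = 1.84 months; or tr = 0, before any postbaseline scan.

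**Method.** Large-sample Kaplan-Meier limit with exponential times. In Model A the removed group has hazard hλ throughout. In Model B its hazard changes from λ to hλ only after removal. In each case λ is solved so that the full-follow-up curve equals 0.5 at 3.7 months. Under 6.4 the removed group is censored at tr, so the curve beyond tr falls at rate λ. At tr = 0 the two models coincide.

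*Worked case, k = 3, h = 2, tr = 0.* Solve 0.925·exp(−3.7λ) + 0.075·exp(−7.4λ) = 0.5, which gives λ = 0.1774.
- Median under 6.4 = ln 2/0.1774 = 3.91 months, a shift of +0.21.
- 6-month value under 6.4 = exp(−6 × 0.1774) = 0.345. Under 7.1 it is 0.925 × 0.345 + 0.075 × 0.119 = 0.328. The shift is +1.7 points.

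*Opposite case, k = 3, h = 0.5, tr = 0.* λ = 0.1961.
- Median under 6.4 = ln 2/0.1961 = 3.54 months, a shift of −0.16.
- 6-month values are 0.308 and 0.327, a shift of −1.85 points.

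| k = 3 | Median shift, months | 6-month shift, points |
|---|---|---|
| h = 2, day 56 (A / B) | +0.09 / +0.12 | +1.0 / +1.3 |
| h = 2, tr = 0 | +0.21 | +1.7 |
| h = 1, either time | 0 | 0 |
| h = 0.5, day 56 (A / B) | −0.09 / −0.08 | −1.4 / −1.2 |
| h = 0.5, tr = 0 | −0.16 | −1.85 |

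**Scale.** 6-month rPFS at a 3.7-month median is exp(−ln 2 × 6/3.7) = 0.325. The 95% half-width at n = 40 is 1.96 × √(0.325 × 0.675/40) = 0.145, or 14.5 points.

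**Why these figures are upper bounds for the assumed inputs.** The model lets 7.1 follow everyone to progression, but new therapy ends scans and leads to censoring there too. It also counts no deaths after removal, whereas a death found within two scan intervals, 2 × (28 × 2 + 7) = 126 days, would still be an rPFS event. Duration of response and time to symptomatic progression were not quantified.

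**The case against.** The strongest reply is that 6.4 never says procedures stop; that is inferred from 7.2 and footnote b. Section 7.1 puts everyone who stops study intervention into follow-up, and a removed participant has stopped it. The scan and symptom-check stopping rules list withdrawal of consent, not removal. Footnote b does not define study withdrawal as including removal by the site or sponsor. Section 7.2.1 even sends participants who are discontinued from the study back to the Schedule of Activities. Sections 6.2.1 and 6.7.2 refer readers to Section 7 for discontinuation criteria, 6.4 requires discussion with the sponsor first, and 7.2 is broad enough to cover removal for noncompliance.

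Much of this stands. It shows that loss of scans is one reading and not a certainty, and that 6.4 and 7.2 are compatible. The triggers also overlap without being identical, since 7.1 adds noncompliance with procedures.

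It does not remove the conflict. Section 7.2.1 deals only with inadvertent enrollment. The cross-references do not override a sentence in 6.4 that states a mandatory outcome. The sponsor discussion has no stated rule to apply.

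Two stronger inferences are tempting. A reader might conclude that rPFS is overstated. That follows only if removed participants are assumed to do worse; h = 0.5 reverses the sign, and the documents support neither direction. A reader might also conclude that confirmed responses are lost and power falls. The documents do not support this: drug stops under both sections, and SAP 6.7.1 counts response evaluations only through the short-term follow-up visit in either case.

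**Conclusion.** The inconsistency is real and minor. Followed literally, 6.4 can end imaging, symptomatic-progression checks and survival contacts that 7.1 would continue, and the resulting censoring of rPFS, duration of response and time to symptomatic progression may be informative.

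With 0 to 3 of 40 removed, a hazard ratio of 0.5 to 2 and a 3.7-month median, all assumed or borrowed, the shift is at most about 0.2 months in median rPFS and about 2 points at 6 months. It is zero if removal is unrelated to prognosis. Both figures are small beside the sampling error, and the endpoints are secondary and descriptive.

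OS is affected only where the vital-status search fails, since under Section 7.3 site personnel or a third party "will attempt to collect the vital status of the participant within legal and ethical boundaries for all participants who initiate treatment". No OS effect was quantified. ORR and its decision rule are unaffected.

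**What to change.** In Section 6.4, replace *discontinued from the study* with *discontinued from study intervention*. Add one sentence: tumor assessments, symptomatic-progression checks and survival follow-up continue per Section 7.1 unless the participant withdraws consent.

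The cost is a few words at the next amendment. No new procedures are needed, because 7.1 and the Schedule of Activities already provide for this follow-up.
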